### 14.3 Medication Diary

**OTHER MEDICATIONS TAKEN**

If you take a daily medication (prescribed or otherwise), please use one line per drug and indicate the start and stop dates under the "Date(s) Taken" section (i.e., 6/2/09 - 6/5/09).

Study Participant Initials \_\_\_\_\_ Date \_\_\_\_\_

FOR STUDY TEAM USE ONLY	
Staff Initials:	
# pills/caps/tabs dispensed:	# pills/caps/tabs at day 15-21 (PK study)
# pills/caps/tabs that should have been taken:	
Discrepancy Notes:	

## DOSING LOG

For each dose take:

Please indicate the date, amount taken and any comments.

Date	Amount Taken		Comments
	Ribociclib	Letrozole	
Ex:	6/1/20	2	1
Day 1			vomited hour later
Day 2			
Day 3			
Day 4			
Day 5			
Day 6			
Day 7			
Day 8			
Day 9			
Day 10			
Day 11			
Day 12			
Day 13			
Day 14			
Day 15			
Day 16			
Day 17			
Day 18			
Day 19			
Day 20			
Day 21			
Day 22			
Day 23			
Day 24			
Day 25			
Day 26			
Day 27			
Day 28			

**Study Participant  
Self-Administration  
Study Drug Diary**

Participant Identifier: \_\_\_\_\_  
Protocol #: \_\_\_\_\_  
Your MD \_\_\_\_\_ Phone \_\_\_\_\_  
Your RN \_\_\_\_\_ Phone \_\_\_\_\_

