Study Design	
This prospective, multicenter, cohort study will assess ribociclib (600 mg PO daily) pharmacokinetics and pharmacogenomics in female patients with HR+/HER2- metastatic breast cancer. This design will be used for two independent, race-based cohorts: 18 African American/Black patients and 18 Non-Hispanic White patients. Women are eligible if they are older than 18, have HR+/HER2- mBC and are candidates for treatment with a CDK 4/6 inhibitor and endocrine therapy. Patients are ineligible if currently prescribed a medication that inhibits or induces the CYP3A isoenzymes, have baseline electrocardiogram abnormalities, or are otherwise considered to be ineligible for ribociclib. Participants will provide serial blood samples during the first cycle. Plasma samples will be analyzed via mass spectrometry to characterize the pharmacokinetics (e.g., <math>AUC_{0-24}</math>, <math>C_{max}</math>). Pharmacogenetic testing will be performed using the PharmacogenoScan™ microarray, which tests 4,627 markers in 1,191 genes, including variants in CYP3A4 and CYP3A5.
 
The primary outcome is powered to detect a minimum clinically meaningful change, a 2-fold change in <math>AUC</math>, which is less than the 3.2-fold change seen in the mentioned CYP3A drug interaction pharmacokinetic study. Based on CYP3A5 allelic frequencies, a sample size of 36 will provide 80% power to independently test the primary outcome in the two race-based cohorts.

Multi-Institutional Trial Management	
Personnel
 
At each site, personnel dedicated to this protocol will be:
 
 
- A study PI
 
- A research coordinator
 
- A data manager
 

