### **1.2.2 Pharmacokinetics**

According to the FDA label for ribociclib, repeated 600 mg once daily administration, steady-state was achieved after 8 days; the time to reach maximum concentration is between one and four hours after administration of ribociclib; the half-life of ribociclib is 32 hours (14).

The FDA label indicates clinical activity is primarily due to the parent drug and ribociclib is metabolized to other compounds that have a negligible contribution on clinical activity. The primary metabolic pathways of ribociclib include oxidation, N-acetylation, sulfation, cysteine conjugation, glycosylation, and glucuronidation (14). Ribociclib is the major circulating drug in plasma, accounting for 44%, however there is a possible contribution to ribociclib effect from circulating metabolites: M13 represents 22% of ribociclib exposure, M4 accounts for 20% and, M1 for 15% (14). Ribociclib is eliminated mainly via feces with a small contribution from the renal route (14).

Ribociclib undergoes hepatic metabolism mainly via CYP3A (14). Ritonavir is a strong CYP3A inhibitor, when ritonavir was given in combination with ribociclib there was an increase of the maximum concentration ( $C_{max}$ ) and the area-under-the-curve (AUC) of ribociclib increased by 1.7 and 3.2-fold, respectively (14, 15). Ribociclib in combination with erythromycin, a moderate CYP3A inhibitor, the  $C_{max}$  and AUC of the CDK 4/6 inhibitor increased by 1.3 and 1.9-fold, respectively (14). The opposite effect in ribociclib concentrations was noted with CYP3A inducers, such as rifampicin (14).

\* The magnitude of extrahepatic FMO1 contribution is unknown

James, A.D., et al. *Pharmacol Res Perspect.* (2020).

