## 2.5 Exploratory Endpoints

4. Correlations between toxicities based on the Common Terminology Criteria for Adverse Events-Patient Reported Outcomes (CTCAE-PRO) questionnaire and ribociclib pharmacokinetic properties (e.g., AUC,  $C_{max}$ ,  $C_{min}$ ).
5. Correlation between candidate pharmacokinetic genes (e.g., *CYP3A4*, *overall CYP3A phenotype*) and pharmacokinetic properties (e.g., AUC,  $C_{max}$ ,  $C_{min}$ ).
6. Correlation between candidate pharmacodynamic variants or genes (e.g., Duffy antigen receptor) and toxicity (e.g., change in white blood cells [WBC]).

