#### **4.3.8 Laboratory Samples**

Laboratory samples for this study will be assessed using the certified laboratory at the Investigators' institutions or at a clinical laboratory such as Quest or LabCorp and these data will be used for all data analysis. The Principal Investigator or sub-Investigator will review, initial, and date all laboratory results and electrocardiograms. Any laboratory value outside the reference range that is considered clinically significant by the Investigator will be followed as appropriate. Clinically significant laboratory values will be recorded as AEs if they meet the criteria as specified in Section 8.1.

Hematology samples (complete blood count [CBC]) will be collected and assessed using a certified laboratory. The Investigator will review, initial, and date all laboratory results. Any laboratory value outside the reference range stated in the inclusion criteria will

preclude the patient from study participation. Comprehensive metabolic panel (CMP) to include: albumin, alkaline phosphatase, ALT, AST, blood urea nitrogen (BUN), creatinine, electrolytes (sodium, potassium, calcium, chloride, bicarbonate), glucose, and total bilirubin. Any laboratory value outside the reference range stated in the inclusion criteria will preclude the patient from study participation. The CBC and CMP are performed per standard clinical practice and are not drawn specifically for research purposes.

Serial blood samples for pharmacokinetic and pharmacogenomic studies will be obtained during cycle one, between days 8 and 16 in the Georgetown University Clinical Research Unit, or locally at the enrolling site. Blood samples will be collected immediately prior to the ribociclib dose, and  $0.5\text{hr} \pm 5\text{min}$ ,  $1\text{hr} \pm 5\text{min}$ ,  $2\text{hr} \pm 15\text{min}$ ,  $4\text{hr} \pm 15\text{min}$ ,  $6\text{hr} \pm 15\text{min}$  after the daily dose of ribociclib. Samples will be collected in the Georgetown University Clinical Research Unit, or at the local site and shipped to the National Institute of Health to process and analyze the data.

Frozen whole blood will be used to isolate DNA via the Wizard® Genomic DNA Purification Kit (Promega). This assay is able to yield 250-500 $\mu\text{g}$  from 10mL of whole blood. The Tissue Culture and Biobanking Shared Resource (TCBSR) will perform DNA isolation in batches. Isolated DNA can then be used for pharmacogenomic testing.

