### **5.3.1 Ribociclib**

Commercially available Ribociclib 600 mg (3 x 200 mg tablets by mouth) QD on days 1 to 21 of a 28-day cycle, followed by 7 days off ribociclib (Days 22 to 28).

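### Neither the protocol nor the patient diary requires or records the time from the previous ribociclib dose to the pre-dose PK sample, so departures from a 24 h interval add error to AUC that can be corrected only approximately

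*Combined protocol and SAP*

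**What the plan says.** Section 4.3.8 states that "Blood samples will be collected immediately prior to the ribociclib dose", and then at 0.5, 1, 2, 4 and 6 h afterwards. The post-dose draws carry windows of 5 or 15 minutes. Section 4.1 and Table 14 give the same schedule. The pre-dose draw has no window relative to the dose before it.

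Section 5.3.1 gives ribociclib "QD on days 1 to 21 of a 28-day cycle" without a time of day, and the diary's instruction is simply daily dosing. The Appendix 14.3 dosing log tells the patient: "Please indicate the date, amount taken and any comments". Section 5.2 measures compliance by counting what remains, and the PROMIS adherence items in Appendix 14.1 ask for no clock time.

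The primary endpoint (section 2.2) is ribociclib AUC at the cycle 1 day 8-16 visit, and the synopsis names AUC0-24. Cmin appears in the rationale (section 1.5) and in the exploratory correlations (section 2.5), but not in the secondary PK list (section 2.4).

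**The concern.** A steady-state AUC over 24 h presumes that the preceding dose was taken about 24 h earlier. If the gap is shorter, residual drug raises every concentration on the PK day. If it is longer, for instance because a dose was left out before the visit, every concentration falls. Neither change has anything to do with CYP3A5.

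A 6 h series, with lunch provided at the research unit (section 12.3), makes a daytime dose on the PK day likely. A woman who normally doses at another hour could therefore arrive with a gap well away from 24 h. Because the last sample is at 6 h, the remaining 18 h of AUC0-24 must be inferred. One ordinary way is to use the pre-dose level as the 24 h level, which is valid only if the gap was 24 h.

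At stake is avoidable error in the primary endpoint. One phenotype group in each cohort may hold only about three women, so such errors may not average out. If the dose time is not recorded, neither the size nor the direction of a patient's error can be seen directly.

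**Working it through.** The plan gives no figure for dose-timing error, so there is none to reproduce.

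**Inputs from the documents**
- Section 1.2.2: "the half-life of ribociclib is 32 hours", "steady-state was achieved after 8 days", and "the time to reach maximum concentration is between one and four hours after administration of ribociclib".
- Section 5.3.1: a nominal 24 h dosing interval.
- Section 9.1: planning SD of log2 AUC 0.75; target a 2-fold change, which is 1.0 on the log2 scale.
- Section 3.3: a smaller phenotype group of at least 3 among 18, taken here as 3 against 15.

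**Assumptions**
- Gaps *g* of 12, 16, 20 and 36 h.
- One-compartment linear kinetics at steady state. Eight days is 192/32 = 6 half-lives, or 1 - 2^(-6) = 98.4% of steady state.

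**Step 1: effect of the gap.** With k = ln2/32 per hour, and relative to a 24 h gap:
- pre-dose ratio = 2^((24-g)/32)
- AUC0-24 ratio = (1 - 2^(-24/32)) + 2^(-g/32) = 0.4054 + 2^(-g/32)

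| Gap | Pre-dose ratio | AUC0-24 ratio |
|---|---|---|
| 12 h | 1.297 | 0.4054 + 0.7711 = 1.1765 |
| 16 h | 1.189 | 0.4054 + 0.7071 = 1.1125 |
| 20 h | 1.091 | 0.4054 + 0.6484 = 1.0538 |
| 24 h | 1.000 | 0.4054 + 0.5946 = 1.0000 |
| 36 h | 0.771 | 0.4054 + 0.4585 = 0.8639 |

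**Step 2: sensitivity.**
- Adding first-order absorption with Tmax from 1 to 4 h gives +17.6% to +18.0% for AUC0-24 at 12 h. With an assumed absorption rate of 1.5 per hour, the 12, 16 and 20 h ratios are 1.179, 1.114 and 1.055.
- Varying the half-life over an assumed 24 to 40 h at a 12 h gap gives +41% to +23% for the pre-dose level and +21% to +15% for AUC0-24.
- If AUC0-24 is completed by using the pre-dose value as the 24 h value, the error at a 12 h gap is about +22%.

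**Step 3: correction without the dose time.** The measured pre-dose level carries the residual-drug information: AUCss = AUC0-24/(1 - e^(-24k)) - Cpre/k. At a 12 h gap and a true half-life of 32 h, in units where the dose adds 1:
- Cpre = 0.7711/0.4054 = 1.902
- AUC0-24 = 2.902 x 0.4054/0.02166 = 54.3, against a true steady-state value of 1/0.02166 = 46.2

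Using the right k removes the error. Using 24 h gives 54.3/0.5 - 1.902/0.02888 = 42.8, or -7%. Using 40 h gives 54.3/0.3402 - 1.902/0.01733 = 49.9, or +8%. This treats AUC0-24 as observed. Here its last 18 h are themselves extrapolated, and 6 h of sampling says little about a 32 h half-life in an individual.

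**Step 4: weight in the primary comparison.**
- One 12 h patient among three: 1.179^(1/3) = 1.056, or +5.6%. On the log2 scale this is 0.238/3 = 0.079.
- Two such patients: 1.179^(2/3) = 1.116, or +11.6% (0.158 on the log2 scale).
- Standard error at 3 against 15: 0.75 x sqrt(1/3 + 1/15) = 0.47.
- The shifts are therefore about 0.17 and 0.33 standard errors.
- If half of all patients have a 12 h gap unrelated to phenotype, the SD becomes sqrt(0.75^2 + 0.25 x 0.2345^2) = 0.759. Normal-approximation two-sided power at 3 against 15 falls from 55.9% to 54.9%. (The distance of that baseline from the plan's 80% is a separate matter.)
- If the 12 h gap occurred in every patient of one phenotype group and in none of the other, a true difference of 1.0 would read as 1.23 or 0.77.

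**The case against.** The strongest reply is that the gap lengths are hypothetical. The documents mention neither evening dosing nor a morning PK visit, and nothing suggests that the hour of dosing depends on CYP3A5 phenotype. In expectation this is noise, and Step 4 shows that it is small against the planning SD. All of that stands.

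It can also be said that the time may be captured elsewhere. CRF pages and visit worksheets are not in the documents, the log has a free-text comments column, drug accountability takes place before the PK studies, and section 8.3.1 counts taking drug at the wrong time as a medication error to be reported. These are partial safeguards. With no dosing time set, there is no wrong time to detect, and none of them asks for the last dose time. The diary is also not aligned with the PK visit: its staff box places the PK pill count at days 15-21, whereas the visit falls on days 8-16.

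Three stronger readings are tempting, and the documents support none of them:
- **Exposure is biased upward.** The sign depends on the gap. A patient who omits the previous evening's dose is biased downward.
- **The error cannot be repaired later.** Step 3 shows an approximate repair from the measured pre-dose level. It needs each patient's elimination rate, and a common rate sits badly with the hypothesis that CYP3A5 status alters metabolism.
- **One mistimed patient decides the primary comparison.** A shift of 0.17 standard errors does not do that.

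**Conclusion.** The point holds as a gap in design and data capture. The plan as written does not secure the time since the previous dose, which is an input to a 24 h AUC built from 0-6 h sampling.

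For an individual patient the error in AUC0-24 could run from about +18% (12 h gap) to about -14% (36 h gap), given a 32 h half-life and linear kinetics. Gaps of 16 and 20 h give about +11% and +5% to +6%. How often such gaps would occur cannot be judged from the documents. For the trial, the likely consequence is a little extra noise, plus the possibility of chance imbalance in a group of about three. Cmin is affected more in proportion, but it is only exploratory. The point is worth acting on because the remedy costs almost nothing and the information is hard to recover afterwards.

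**What to change.** - Add a clock-time column to the Appendix 14.3 dosing log.
- Add the date and time of the last ribociclib dose before the visit to the PK CRF.
- Schedule the PK visit, where possible within days 8-16, so that the pre-dose draw falls about 24 h after the patient's previous dose.
- State in section 9.2 that AUC and Cmin will be derived from actual elapsed times, including the time since the previous dose.
- Flag patients whose gap is far from 24 h, with a threshold fixed before analysis, and repeat the primary comparison without them or with a model-based correction.

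The protocol need not prescribe an hour of dosing. Recording the time and fitting the visit to it is enough.

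The cost is one diary column, one CRF field, a few sentences in the analysis plan and an occasional reschedule inside the existing window.

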**STUDY DRUG INSTRUCTIONS:**

**Study Drug A: Ribociclib**  
**Study Drug B: Letrozole**

**How Much:** 600 mg  
**How Often:** Daily

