## **4 Study Design**

### **4.1 Study Design**

[figure not shown]
Two separate cohorts, based on self-identified race, will be followed prospectively during this study. Eighteen African Americans/Blacks and 18 Non-Hispanic White women with metastatic HR+/HER2- advanced breast cancer will be enrolled. Patients will receive ribociclib 600 mg oral (PO) daily for 21 consecutive days of 28-day cycles and endocrine

therapy with either letrozole or fulvestrant. Fulvestrant 500 mg intramuscular (IM) will be administered on days 1, 15, 29 of cycle one, and then monthly. Letrozole 2.5 mg oral daily continuously. If premenopausal women have not undergone bilateral salpingo-oophorectomy, they will receive a luteinizing hormone-releasing hormone (LHRH) agonist (e.g., goserelin leuprolide) for ovarian suppression in combination with fulvestrant or letrozole and ribociclib.

The Clinical Research Unit (CRU) is located in Georgetown University (7 East, Main Hospital, [name], Washington DC) and it provides specialized institutional resources in which clinical investigators can observe and study human physiology and treat diseases with innovative approaches. Subjects may have the visit between day 8 and day 16 of cycle 1 at the CRU or locally at the site.

Between days 8 and day 16 (i.e., steady state) of cycle 1 of ribociclib and fulvestrant, participants will provide serial blood samples at the Georgetown University Clinical Research Unit or locally at the enrolling site, immediately prior to the ribociclib dose, and 0.5hr ± 5min, 1hr ± 5min, 2hr ± 15min, 4hr ± 15min, 6hr ± 15min after the daily dose of ribociclib. Plasma samples will be analyzed at the National Cancer Institute via mass spectrometry to facilitate the measurement of pharmacokinetic properties. A blood sample will be utilized for pharmacogenetic testing on the PharmacogenoScan™ (ThermoFisher) microarray, which includes 51 variants in *CYP3A4* and 22 in *CYP3A5*.

Per FDA labeling, periodic electrocardiogram will be obtained prior to the first cycle, between C1D8-C1D16, at the start of the second cycle, and as clinically indicated. Additionally, a complete blood count (CBC) with differential and comprehensive metabolic panel (CMP) will be obtained at baseline (medical visit prior to C1D1), between C1D8-C1D16, at the start of the second cycle

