## **6 Study Procedures**

### **6.1 Schedule of Events**

Screening assessments are to be conducted within 28 days prior to initiating protocol therapy unless otherwise specified. CBC with differential and biochemical profile (sodium, potassium, calcium, chloride, bicarbonate, BUN, creatinine, AST, ALT, total bilirubin, albumin, alkaline phosphatase) assessments must be done within 28 days prior to initiating protocol therapy, between day 8-16 of cycle 1, and prior to initiation of cycle 2.

Table 14. Study Calendar: Patients will be followed for one cycle

Study procedure/task	Screening a	Treatment cycle is 28 days	End of study b
Study day	≤ 28 days prior to study entry	Cycle 1 Day 8 - 16	
Procedures			
Eligibility criteria c	X		
Informed consent d	X		
Clinical visits e	X	Per routine clinical practice	
Adverse Events		X	X
CYP3A5 Screening f	X		
Treatments g			
Ribociclib		600 mg PO once daily for 21 days, followed by a 7-day rest period to complete a 28-day treatment cycle	
Fulvestrant		500 mg IM injection on days 1 and 15	
Letrozole		2.5 mg PO daily	
Goserelin		3.6 mg SQ every 28 days or 10.8 mg SQ every 12 weeks	
Leuprolide depot		3.75 mg IM every 28 days or 11.25 mg IM every 12 weeks	
Tests			
Blood draw for pharmacogenomic studies		X	
Serial blood draws for pharmacokinetic studies			

 
Immediately prior to the ribociclib dose, and 0.5hr ± 5min, 1hr ± 5min, 2hr ± 15min, 4hr ± 15min, 6hr ± 15min after the daily dose of ribociclib.
 
		X	
Electrocardiogram h	X	X	X
CBC with differential and CMP i	X	X	X
Pregnancy Test j	X		
NCI CTCAE PRO questionnaire k	X	X	X
Adverse event monitoring log	X	X	X
Medication adherence PROMIS questionnaire and drug accountability		X	X

a Screening: All assessments should be performed within 28 days prior to study entry. Study entry will be defined by confirmation of eligibility.

b This visit will occur prior to initiation of cycle 2 (e.g., 29th day of the study, plus or minus 3 days)

c Eligibility Criteria Evaluation: Patients must meet all of the eligibility criteria reported in the protocol

d Informed Consent: Must be obtained prior to undergoing any study-specific procedures.

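### The Appendix 14.3 patient diary tells the patient to take ribociclib daily without stating the 21-days-on, 7-days-off schedule (minor; a pill-count label also needs correcting)

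*Combined protocol and SAP*

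**What the plan says.** The operative sections agree on the ribociclib schedule. Section 4.1 specifies "ribociclib 600 mg oral (PO) daily for 21 consecutive days of 28-day cycles". Section 5.3.1 has the drug taken "QD on days 1 to 21 of a 28-day cycle, followed by 7 days off ribociclib (Days 22 to 28"). Table 14 in section 6.1 gives "600 mg PO once daily for 21 days, followed by a 7-day rest period to complete a 28-day treatment cycle".

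Appendix 14.3 is a self-administration diary held by the patient. Its Study Drug Instructions name ribociclib and letrozole and then give "How Much: 600 mg" and "How Often: Daily". The dose can only refer to ribociclib, because letrozole is 2.5 mg. The dosing log has rows for days 1 to 28, with columns for both drugs, and asks the patient: "Please indicate the date, amount taken and any comments". The words of Appendix 14.3 nowhere mention days 1-21 or an off-week.

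The block for study staff has a count labelled "pills/caps/tabs at day 15-21 (PK study"). Sections 2.2, 4.1 and 4.3.8 and Table 14 all put the PK visit on days 8-16 of cycle 1.

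**The concern.** The rest week is the one feature of this regimen that a patient would not guess, and the form she reads at home leaves it out. If she took the instruction literally and had tablets left, she would carry on into days 22-28.

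Two things would be at stake. The first is safety: she would lose the week off a drug for which section 1.2.4 describes neutropenia as dose-dependent and suggests the same for QTc prolongation. The second is the later of the two comparisons that section 2.4 lists for QTc and for neutropenia, ALT and AST. It runs from baseline to the visit before cycle 2, and Table 14 footnote b times that visit as follows: "This visit will occur prior to initiation of cycle 2 (e.g., 29th day of the study, plus or minus 3 days"). An assessment meant to follow a rest week would then be made on or just after treatment.

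The pill-count label is a separate and smaller matter. Read literally, it sends staff to count tablets for the PK study at a time that mostly falls after the PK visit.

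**Working it through.** The plan states no figure to reproduce here. The check compares sections and does simple counting.

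**1. Schedule.** Sections 4.1 and 5.3.1 and Table 14 say 21 days on and 7 off. The Appendix 14.3 instruction gives a dose and a frequency but no days. It is incomplete rather than false, since daily is correct on days 1-21.

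**2. Could a patient dose in the off-week?** Section 5.3.1 gives 3 tablets of 200 mg per dose. The protocol schedule needs 21 x 3 = 63 tablets, or 63 x 200 = 12,600 mg. The number dispensed is not stated, so it has to be assumed.
- If 63 tablets are dispensed, they cover 63/3 = 21 dosing days. A patient who misses no dose runs out on day 21 and takes 0 off-week doses. Each day missed in days 1-21 leaves 3 tablets, enough for one off-week dose. The total stays at or below 12,600 mg.
- If at least 28 x 3 = 84 tablets are to hand, all 7 off-week doses are possible. No section describes such a supply.

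**3. What drug level would result?** Section 1.2.2 gives steady state after 8 days and a half-life of 32 hours. Assuming first-order decline, the fraction left 24 hours after a dose is 2^(-24/32) = 0.595. That applies between any two daily doses, including those on days 8-21. Carrying on with the same dose at the same interval therefore holds the steady-state level and does not raise it. Under the protocol schedule, a day-29 visit falls 8 x 24 = 192 hours after the day-21 dose, leaving 2^(-192/32) = 2^(-6) = 0.0156. Off-week dosing would replace a washout with an ordinary on-treatment level.

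**4. Which assessments are exposed?**
- Primary AUC (section 2.2): taken on days 8-16, before day 22, so it is not affected.
- The section 9.2 two-group comparison of change in QTc and neutrophil count by CYP3A5 phenotype: it uses baseline and C1D8-C1D16, so it is not affected.
- The section 2.4 comparisons of baseline with the visit before cycle 2: exposed. The visit may fall on days 26 to 32 (29 plus or minus 3). At a day-26 visit, at most 4 off-week doses (days 22-25) can have been taken on earlier days.

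**5. Pill-count window.** Days 8-16 are 9 days and days 15-21 are 7 days. They share only days 15 and 16. So 9 - 2 = 7 of the 9 permitted PK days (78%) fall outside the label, and 7 - 2 = 5 of the 7 labelled days fall after the PK window has closed.

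**The case against.** The case for leaving the form alone is reasonable. Daily is a frequency, and the synopsis uses the same shorthand. Section 5.3 has the oncologist prescribe commercial product, so the diary is not the dosing authority. The log needs 28 rows because letrozole is continuous. Section 5.2 requires drug accountability at every cycle 1 visit. All of this stands, and it makes the error unlikely. It does not remove the gap: accountability at the end of the cycle would reveal off-week dosing only after it had happened, and the synopsis, unlike the diary, is not an instruction to a patient.

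A reader might infer more than the documents support, in five ways.
- *That the log leaves days 22-28 unmarked for ribociclib.* The layout of the form did not survive in the machine-read text, and shading or struck-out cells would not appear there. Only the absence of wording can be established. For the same reason, nothing is claimed about whether letrozole has its own dose line.
- *That the form implies a 33% overdose* (84/63 = 1.33). This needs a tablet supply that no section states.
- *That the day-29 level would be 38 times too high* (0.595/0.0156 = 38). The ratio sets an ordinary trough against a near-zero washout level. It does not describe exposure above that of days 8-21, and the trial takes no PK sample at that visit.
- *That section 1.2.4 shows how much harm would follow.* The study cited there compared 600 mg on days 1-21 with continuous 400 mg, and grade 3/4 neutropenia was 62% against 36%. That supports an effect of daily dose. It does not test loss of the rest week at 600 mg.
- *That the pill-count label undermines the adherence check behind the AUC.* Section 5.2 already requires a count at each cycle 1 visit, section 4.1 places accountability before the PK studies, and the daily log also records doses. The label is clerical.

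**Conclusion.** The point holds as a minor correction to a patient form. The ribociclib instruction in Appendix 14.3 omits the days 1-21 limit and the off-week that sections 4.1 and 5.3.1 and Table 14 require. Harm depends on a patient following the form over her prescription while holding leftover tablets. How many would do so is unknown, and probably few. With 63 tablets dispensed (an assumption), the number of off-week doses cannot exceed the number of days missed earlier. If it happened, she would lose the rest week at levels no higher than those of days 8-21, and the pre-cycle-2 QTc, neutrophil and ALT/AST comparisons might be affected. The primary AUC is not.

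Confidence in the dosing-instruction point is moderate, because the original layout of the form cannot be seen. The pill-count label plainly disagrees with the PK window but changes no procedure.

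**What to change.** In the Study Drug Instructions, write: *Ribociclib 600 mg (3 x 200 mg tablets) once daily on days 1-21; none on days 22-28.* Mark the ribociclib cells of the log for days 22-28 as off, if the original form does not already do so. Keep all 28 rows for letrozole. In the same revision, relabel the staff pill count as *day 8-16 (PK study)*.

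The cost is one form revision with IRB approval. It adds no visits, samples or data items and changes no analysis.
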